#### **3.1.1.1 Definition of Dose-Limiting Toxicity**

For dose-escalation purposes, any one of the following events will be considered a DLT if it occurs during the DLT assessment window, unless clearly attributed to another identified etiology by the investigator (e.g., cancer progression):

- $\geq 15\%$  decrease from baseline in LVEF or  $\geq 10\%$  decrease to less than a 50% LVEF
- Grade  $\geq 3$  non-hematologic toxicity with the following exceptions:
  - Grade 3 nausea, vomiting, or diarrhea that resolves to Grade  $\leq 1$  with standard-of-care therapy in  $\leq 7$  days
  - Grade 3 fatigue that resolves to Grade  $\leq 2$  in  $\leq 7$  days
  - Grade 3 elevation of serum hepatic transaminase (ALT or AST) without an increase in direct bilirubin  $> 2 \times$  upper limit of normal (ULN) or clinical jaundice and lasting  $< 7$  days
  - Grade 3 laboratory abnormalities that are asymptomatic and considered by the investigator not to be clinically significant
- Grade  $\geq 4$  neutropenia (ANC  $< 500$  cells/ $\mu$ L) lasting  $> 7$  days
- Grade  $\geq 3$  febrile neutropenia
- Grade  $\geq 4$  anemia

- Grade  $\geq 4$  thrombocytopenia
- Grade 3 thrombocytopenia associated with clinically significant bleeding
- Any increase in hepatic transaminase (ALT or AST)  $> 3 \times$  baseline in combination with either an increase in direct bilirubin  $> 2 \times$  ULN or clinical jaundice, in the absence of cholestasis or other contributory factors (e.g., worsening of metastatic disease, concomitant exposure to known hepatotoxic agent, or documented infectious etiology).

This is suggestive of potential drug-induced liver injury (according to Hy's Law) and will be considered a DLT.

### **3.1.1.2 Starting Dose, Dose-Escalation Rules, and Determination of the Maximum Tolerated Dose**

The starting dose of DHES0815A is 0.6 mg/kg administered by IV infusion Q3W to patients in the first cohort. The dose may be increased by up to 100% of the preceding dose level for each successive cohort until a safety signal (defined as a DLT in 1 patient or study drug-related Grade  $\geq 2$  major organ adverse events (unless present at baseline) in at least 2 patients during the DLT assessment window in a given cohort) is observed. Once a safety signal has been observed in a given cohort, the dose may be increased by up to 50% of the preceding dose level for each successive cohort. Intrapatient dose escalation may be allowed for some patients (see Section 3.1.1.3).

Dose escalation of DHES0815A will occur in accordance with the rules listed below.

- A minimum of 3 patients will initially be enrolled in each cohort.
- If none of the first 3 DLT-evaluable patients experiences a DLT, enrollment of the next cohort at the next highest dose level may proceed.
- If 1 of the first 3 DLT-evaluable patients experiences a DLT, the cohort will be expanded to 6 patients. If there are no further DLTs in the first 6 DLT-evaluable patients, enrollment of the next cohort at the next highest dose level may proceed.
- If 2 or more DLT-evaluable patients in a cohort experience a DLT, the MTD will have been exceeded and dose escalation will stop. An additional 3 patients will be evaluated for DLTs at the preceding dose level, unless 6 patients have already been evaluated at that level. However, if the dose level at which the MTD is exceeded is  $\geq 15\%$  higher than the preceding dose level, 6 patients may be evaluated at an intermediate dose level.
- If the MTD is exceeded at any dose level, the highest dose at which fewer than 2 of 6 DLT-evaluable patients (i.e.,  $< 33\%$ ) experience a DLT will be declared the MTD.
- If the MTD is not exceeded at any dose level, the highest dose administered in this study will be declared the maximum administered dose (MAD).
- As long as the MTD has not been exceeded, additional patients may be enrolled at a given dose level in a given arm to explore factors influencing adverse events or to accumulate additional safety data.

Relevant demographic, adverse event, laboratory, dose administration, and PK (if available) data will be reviewed prior to dose-escalation decisions, which will be made by the Sponsor Medical Monitor in consultation with the Principal Investigators and a committee composed of the following Sponsor representatives: Medical Monitor and clinical safety scientist, with consultation from the statistician, clinical pharmacologist, and clinical trial leader. On the basis of a review of real-time safety data and available preliminary PK data, dose escalation may be halted or modified by the Sponsor as deemed appropriate.

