### **3.1.1 Dose-Escalation Stage**

Approximately 24–30 patients will be enrolled in the dose-escalation stage. Cohorts of 3–6 patients each will be treated at escalating doses of DHES0815A in accordance with the dose-escalation rules described below. The starting dose of DHES0815A is based on nonclinical safety assessments and will be no higher than 0.6 mg/kg IV Q3W (see Section 3.3.2 for more details). For added safety during dose escalation, treatment will be staggered such that the first patient treated at each dose level will receive his or her first infusion at least 1 day prior to subsequent patients in that cohort. In addition, cohorts may be expanded even in the absence of dose-limiting toxicities (DLTs) in order to evaluate non-DLT adverse events further or to collect additional safety or PK data. Intrapatient dose escalation as per Section 3.1.1.3 will be allowed.

Patients will be closely monitored for adverse events during the DLT assessment window, defined as Days 1–21 of Cycle 1. Adverse events identified as DLTs, as defined in Section 3.1.1.1, will be reported to the Sponsor within 24 hours (see Section 5.3.1).

Patients who discontinue from the study prior to completing the DLT assessment window for reasons other than a DLT will be considered non-evaluable for dose-escalation decisions and maximum tolerated dose (MTD) assessments and will be replaced by an additional patient at that same dose level. Patients who receive supportive care during the DLT assessment window that confounds the evaluation of DLTs may be replaced at the discretion of the Medical Monitor.

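### In escalation cohorts of 4 or 5, the written outcome of a single DLT depends on which patient has it, because the 0-DLT and 1-DLT bullets count only the first 3 evaluable patients

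*Combined protocol and SAP*

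**What the plan says.** Three statements make a cohort of 4 or 5 possible. Section 3.1.1 says "Cohorts of 3–6 patients each will be treated at escalating doses of DHES0815A" and lets a cohort be enlarged when no DLT has occurred. Section 3.1.1.2 sets a floor but no ceiling on initial enrollment: "A minimum of 3 patients will initially be enrolled in each cohort". It also adds: "As long as the MTD has not been exceeded, additional patients may be enrolled at a given dose level in a given arm".

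The rules in Section 3.1.1.2 use two different denominators.

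- **0 DLTs, first 3 only:** "If none of the first 3 DLT-evaluable patients experiences a DLT, enrollment of the next cohort at the next highest dose level may proceed".
- **1 DLT, first 3 only:** "If 1 of the first 3 DLT-evaluable patients experiences a DLT, the cohort will be expanded to 6 patients". Escalation may then follow on this condition: "If there are no further DLTs in the first 6 DLT-evaluable patients".
- **2 or more DLTs, whole cohort:** two evaluable patients with a DLT anywhere in the cohort mean that the MTD is exceeded and escalation stops.
- **Safety signal, whole cohort:** a DLT in any one patient of a cohort limits later dose steps to 50%.

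Section 4.2 holds the dose-escalation meeting once the last patient of the cohort has finished the 21-day window, and DLTs in any patient of that cohort are reviewed. The closing paragraph of Section 3.1.1.2 allows the Sponsor to halt or modify escalation on the safety and PK data.

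**The concern.** No bullet covers three clean patients followed by a single DLT in patient 4 or 5. Read literally, the 0-DLT bullet is still met, so the next dose level may open at an observed 1/4 or 1/5. If the same single DLT falls on one of patients 1–3, the cohort must go to 6 first. The count and the dose are the same, but the written consequence differs.

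The term first 3 is also not defined. It could mean order of enrollment, of dosing, or of completing the DLT window. Section 3.1.1 staggers only the first patient of a cohort, by at least one day, and leaves some replacements to the Medical Monitor's discretion. Which three patients count can therefore be disputed in exactly the situation where it decides the outcome.

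At stake is whether, in a first-in-human study, a DLT already observed at the current dose triggers the same protection whichever patient has it.

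**Working it through.** **Inputs.** Cohort size is 3–6 (Section 3.1.1). The bullets are those of Section 3.1.1.2. True DLT rates p are taken from Table 6 (Section 6.1.1). Patients are treated as independent with a common p, and escalation is assumed to follow whenever the bullets permit it.

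**Step 1: reproduce Table 6.** With decisions at exactly 3 and 6,

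P(escalate) = (1−p)³ + 3p(1−p)² × (1−p)³.

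At p = 0.3 this is 0.343 + 0.151 = 0.494, and Table 6 prints 49%. Over the ten rates the formula gives 97.3, 90.6, 70.9, 49.4, 30.9, 17.2, 8.2, 3.2, 0.9 and 0.1%, all matching the table.

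**Step 2: how often order matters, given exactly one DLT.** All positions are equally likely. In a cohort of 4 the DLT lies outside the first three in 1 of 4 orders. In a cohort of 5 it does so in 2 of 5.

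**Step 3: probability of a clean first three and then exactly one DLT.**

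- 4 patients: (1−p)³ × p. At p = 0.3: 0.343 × 0.3 = 10.3%.
- 5 patients: (1−p)³ × 2p(1−p). At p = 0.3: 0.343 × 0.42 = 14.4%.

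**Step 4: P(escalate) under the two readings.**

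- 4 patients, as written: (1−p)³ + 3p(1−p)⁵
- 4 patients, counting all evaluable: (1−p)⁴ + 4p(1−p)⁵
- 5 patients, as written: (1−p)³(1−p²) + 3p(1−p)⁵
- 5 patients, counting all evaluable: (1−p)⁵ + 5p(1−p)⁵

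Counting all means that 0 DLTs permits escalation, 1 DLT leads to expansion to 6 with escalation at 1/6, and 2 or more stops. Differences are in percentage points, from unrounded values.

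| True DLT rate | 4 pts, as written | 4 pts, all | Diff. | 5 pts, as written | 5 pts, all | Diff. |
|---|---|---|---|---|---|---|
| 20% | 70.9% | 67.2% | 3.7 | 68.8% | 65.5% | 3.3 |
| 30% | 49.4% | 44.2% | 5.2 | 46.3% | 42.0% | 4.3 |
| 40% | 30.9% | 25.4% | 5.5 | 27.5% | 23.3% | 4.1 |
| 50% | 17.2% | 12.5% | 4.7 | 14.1% | 10.9% | 3.1 |

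**Step 5: cross-check.** The difference should equal the probability in Step 3 times the chance that completing the cohort to 6 shows a second DLT. At p = 0.3:

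- 4 patients: 0.1029 × (1 − 0.7²) = 0.1029 × 0.51 = 5.2 points.
- 5 patients: 0.1441 × 0.3 = 4.3 points.

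Both agree with the table. They also show why the 10.3% and 14.4% are not the size of the effect: many of those cohorts would still escalate after expansion.

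**The case against.** The strongest reply is that the bullets are not the whole decision process. The 0-DLT bullet permits escalation and does not require it. The meeting in Section 4.2 waits for the whole cohort, so the DLT is known when the decision is made, and the Sponsor may halt or modify escalation. A DLT in patient 4 or 5 is a safety signal and caps the next step at 50%. It also counts toward the 2-or-more stopping rule. All of this stands. A reader might infer that the late DLT is ignored, or that identical data force opposite decisions by enrollment order alone. The documents do not support either reading: the contrast is between a mandatory expansion and a discretionary decision taken with the DLT in view.

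Second, cohorts of 4 or 5 are allowed but not planned. Section 3.1.1 ties the 3–6 range to the rules that follow, and those decide at 3 and 6. The documents give no frequency for intermediate sizes, so it would be wrong to say that such cohorts will occur. This stands too.

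Third, the literal rule is no looser than advertised. A 4-patient cohort reproduces Table 6, a 5-patient cohort is slightly more conservative, and 1/4 (25%) and 1/5 (20%) lie below the under-33% criterion used for the MTD. This shows that no printed figure is wrong. It does not settle the inconsistency. The 4-patient result equals Table 6 because a lone DLT in the fourth patient plays no part in the choice between the 0-DLT and 1-DLT bullets, whereas the adjoining rules count that patient. Discretion does not fill the gap, since neither Section 4.2 nor the closing paragraph of Section 3.1.1.2 says what follows 1/4 or 1/5.

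**Conclusion.** The point holds as an internal inconsistency in the escalation bullets. For exactly one DLT in a cohort of 4 or 5, the written outcome depends on whether the DLT falls among an undefined first 3, and the departure is toward permitting escalation. The stopping bullet, the safety-signal definition and the Section 4.2 review already use the whole cohort.

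The effect is modest: about 3 to 5.5 percentage points in the probability of escalating at true DLT rates of 20–50%. It is conditional on a cohort of 4 or 5 being used, on independent patients with a common DLT rate, and on escalation being taken whenever it is permitted. A cohort of exactly 3 or exactly 6 shows no order effect.

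A reader might also infer that Table 6 is wrong. It is not: it is correct for decisions at exactly 3 and 6. This is a clarification that should be made, not a failure of the escalation scheme.

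**What to change.** Reconcile Sections 3.1.1, 3.1.1.2 and 4.2 so that the same DLT count in a cohort of 4 or 5 leads to the same written decision whichever patient has the DLT. The consistent way is to let the 0-DLT and 1-DLT bullets refer to all DLT-evaluable patients in the cohort at the time of the decision, which is the denominator that the stopping bullet already uses. The undefined first 3 then drops out. Table 6 can stay, with a note that it assumes decisions at 3 and 6.

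The cost is two edited bullets. Only when a lone DLT falls on patient 4 or 5, the change also means 2 more patients (from 4) or 1 more (from 5), within the stated 3–6 cohort size, and a further 21-day DLT window before the next cohort can open.

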### **3.1.1.3      Intrapatient Dose Escalation**

To minimize the exposure of patients to suboptimal doses and to maximize the collection of information at relevant doses, patients may progressively escalate from their current dose of DHES0815A to the highest dose level tolerated by completed cohorts. Patients will need to complete at least three cycles at their originally assigned DHES0815A dose level, as well as at each of the subsequent dose levels, prior to any further dose escalation.

Once the MTD is declared and the RP2D is determined, patients who remain in the study and continue to tolerate the study drug may escalate their dose to the RP2D level or the dose level below the RP2D under their current dosing schedule. The RP2D will be at or below the MTD (or MAD) and determined by the totality of data, including DLTs, safety, activity, and PK data (see Section [3.1.1.2](#)).

All intrapatient dose-escalation decisions will be made by the Sponsor in consultation with the participating investigators and will include assessment of safety data within the treatment cohorts, as well as the totality of the safety data.

*For patients in Cohorts 1–5, please also refer to Section [3.1](#).*

### **3.1.1.4      Continuation of DHES0815A (Cycles $\geq 2$ )**

Patients without a DLT during the DLT assessment window will be eligible to receive additional infusions of DHES0815A at the same dose level at which they were enrolled or at an increased dose as detailed in Section [3.1.1.3](#) (the day of infusion being Day 1 of each cycle), provided that they meet the following criteria for acceptable toxicity and ongoing clinical benefit:

- Acceptable toxicity: All adverse events experienced with prior infusions that were not attributed to constitutional symptoms of the patient's cancer or intercurrent illness must have decreased to Grade 1 or baseline grade on or before the day of the next infusion.

Exceptions on the basis of ongoing clinical benefit may be allowed after a careful assessment and discussion of benefit versus risk with the patient by the investigator and approval from the Medical Monitor. In addition, delay of therapy because of toxicities not attributed to study drug may not require discontinuation

from the study but must be approved by the Medical Monitor. Dose modifications are described in Section 5.1.2.1.

- Ongoing clinical benefit: Patients must demonstrate improvement/stabilization in tumor burden, according to the RECIST v1.1 ([Appendix 3](#)) or demonstrate clinical signs or symptoms of benefit, as judged by the investigator, independent of RECIST.

All tumors assessed at screening must be documented and re-assessed at each subsequent tumor evaluation (see [Appendix 1](#) for tumor assessment schedule). For each patient, the same imaging modality should be used throughout the study.

*For patients in Cohorts 1–5, please also refer to Section 3.1.*

Women of childbearing potential will need to undergo a urine pregnancy test prior to each DHES0815A cycle (patients whose breast tumor produces human chorionic gonadotropin [hCG] and were confirmed not to be pregnant prior to enrollment should be monitored with serum pregnancy tests rather than urine pregnancy tests prior to each cycle of study treatment). If a urine pregnancy test result is positive, patient dosing will be postponed until the result is confirmed by a serum pregnancy test. Patients who are pregnant must permanently discontinue study treatment.

DHES0815A administration will be discontinued in patients who experience a DLT during the DLT assessment window (Days 1–21 of the first cycle) if this toxicity does not return to baseline grade within 14 days. Patients who experience a DLT during the first cycle (Days 1–21) and whose toxicity returns to baseline within 14 days may be restarted at a dose level tolerated by the prior cohort following discussion with the Medical Monitor. A treatment delay beyond 14 days may be acceptable upon discussion with the Medical Monitor (see Section 5.1.2.1).

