#### **5.1.2.2      Management Guidelines for Patients Who Experience Adverse Events**

Guidelines for managing DHES0815A-related toxicities other than the ones specified in [Table 3](#) are as follows:

- For Grade  $\geq 3$  adverse events: DHES0815A treatment should be withheld for Grade  $\geq 3$  DHES0815A-related toxicities that have not recovered to Grade  $\leq 1$  or baseline prior to planned dosing. The next scheduled dose may be delayed by up to 14 days. Longer dose interruptions are only allowed upon discussion with the Medical Monitor. If improvement to Grade  $\leq 1$  or baseline does not occur within 14 days (or a longer interval approved by the Medical Monitor), DHES0815A treatment should be discontinued. If the DHES0815A-related toxicity improves to Grade  $\leq 1$  or baseline, DHES0815A may be restarted at a reduced dose.

The DHES0815A dose in subsequent cycles should be reduced to either the next lowest dose level tested in dose escalation for patients in the dose escalation cohort, or by approximately 25%–50% (upon discussion with the Medical Monitor) for patients in the expansion cohort. No more than two dose reductions are permitted on study.

- For Grade 2 adverse events: DHES0815A treatment should be withheld for Grade 2 DHES0815A-related toxicities that have not recovered to Grade 1 or baseline prior to planned dosing. The next scheduled dose may be delayed by 14 days. Longer dose interruptions may be allowed upon discussion with the Medical Monitor. If improvement to Grade  $\leq 1$  or baseline does not occur within

14 days (or a longer interval approved by the Medical Monitor), DHES0815A treatment should be discontinued. If the DHES0815A-related toxicity improves to Grade  $\leq 1$  or baseline, DHES0815A may be restarted at the current dose.

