**Table 3 Guidelines for Management of Patients Who Experience Specific Adverse Events**

Event	Action to Be Taken
Hematologic toxicity as manifested in any one of the below laboratory abnormalities: 

• Absolute neutrophils <math>< 1500/\text{mm}^3</math>

• Hemoglobin <math>< 8 \text{ g/dL}</math>

• Platelets <math>< 100,000/\text{mm}^3</math>

	

Withhold all study treatment up to 14 days; longer dose interruption may be allowed upon discussion with the Medical Monitor.

Give supportive treatment as clinically indicated per local practice.

Resume DHES0815A treatment if ANC <math>\geq 1500/\text{mm}^3</math>, platelets <math>\geq 100,000/\text{mm}^3</math>, and hemoglobin <math>\geq 8 \text{ g/dL}</math>.

If hematologic toxicity leading to dose hold recurs in consecutive cycles, resume DHES0815A treatment at a reduced dose if ANC <math>\geq 1500/\text{mm}^3</math>, platelets <math>\geq 100,000/\text{mm}^3</math>, and hemoglobin <math>\geq 8 \text{ g/dL}</math>.

If hematologic toxicity leading to dose hold occurs in two consecutive cycles at the reduced dose, discontinue DHES0815A.

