**Table 3 Guidelines for Management of Patients Who Experience Specific Adverse Events (cont.)**

Event	Action to Be Taken
Infusion-related reaction or hypersensitivity Grades 1–2	
Reduce DHES0815A infusion rate or interrupt infusion. Administer supportive care with oxygen, <math>\beta</math>-agonists, antihistamines, antipyretics, or corticosteroids, as appropriate or according to local standard of care, at the investigator's discretion.
 
Monitor patient until complete resolution of symptoms.
 
Patient may continue DHES0815A infusion (in same cycle and subsequent cycles) at the same dose level but at a decreased infusion rate at the investigator's discretion.
 
 
Premedication for infusion reactions (e.g., antihistamines such as diphenhydramine, acetaminophen/paracetamol or corticosteroids) may be given at the investigator's discretion for subsequent infusions.
 
 
In the event of a true hypersensitivity reaction (in which severity of reaction increases with subsequent infusions), discontinue DHES0815A permanently.

Infusion-related reaction or hypersensitivity Grade 3	
Stop DHES0815A infusion.
 
Administer supportive care with oxygen, <math>\beta</math>-agonists, antihistamines, antipyretics, or corticosteroids, as appropriate, at the investigator's discretion.
 
Monitor patient until complete resolution of symptoms.
 
Note: If Grade 3 symptoms included wheezing, hypoxia, generalized urticaria, angioedema or other signs and symptoms indicating anaphylactic reaction, discontinue DHES0815A permanently. For other Grade 3 events, patients may continue DHES0815A (in same cycle and subsequent cycles) at the same dose level but reduced infusion rate at the investigator's discretion.
 
 
Premedication for infusion reactions (e.g., antihistamines such as diphenhydramine, acetaminophen/paracetamol or corticosteroids) should be given for subsequent infusions.
 
 
In the event of a true hypersensitivity reaction (in which severity of reaction increases with subsequent infusions), discontinue DHES0815A permanently.

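### After a Cycle 1 DLT, Section 3.1.1.4 conflicts with Table 3 on the restart dose after a Grade 3 infusion reaction, and with Section 5.1.2.2 and Table 3 on the recovery required

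*Combined protocol and SAP*

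**What the plan says.** Section 3.1.1.4 gives same-dose or higher-dose continuation to patients who had no DLT. For patients with a DLT in Days 1–21 of Cycle 1 it sets a separate rule. Treatment stops "if this toxicity does not return to baseline grade within 14 days". A patient "whose toxicity returns to baseline within 14 days may be restarted at a dose level tolerated by the prior cohort", provided the case has been discussed with the Medical Monitor. It adds: "A treatment delay beyond 14 days may be acceptable upon discussion with the Medical Monitor", with a pointer to Section 5.1.2.1.

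Section 3.1.1.1 counts as a DLT any Grade 3 or higher "non-hematologic toxicity with the following exceptions": certain gastrointestinal events, fatigue, transaminase elevations and asymptomatic laboratory abnormalities. Infusion reactions are not excepted. Several hematologic events are also DLTs, for example "Grade 3 thrombocytopenia associated with clinically significant bleeding".

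Three other places govern re-dosing:

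- **Table 3, Grade 3 infusion-related reaction or hypersensitivity.** Anaphylactic signs mean permanent discontinuation. Otherwise: "For other Grade 3 events, patients may continue DHES0815A (in same cycle and subsequent cycles) at the same dose level", at a slower rate and at the investigator's discretion.
- **Table 3, hematologic toxicity.** Treatment resumes once ANC is at least 1500/mm³, platelets at least 100,000/mm³ and hemoglobin at least 8 g/dL. A reduction appears only in the next step: "If hematologic toxicity leading to dose hold recurs in consecutive cycles, resume DHES0815A treatment at a reduced dose", subject to the same counts.
- **Section 5.1.2.2, related Grade 3 or higher toxicity not covered by Table 3.** If it improves to Grade 1 or lower, or to baseline, "DHES0815A may be restarted at a reduced dose". For escalation patients this is the next lowest tested level.

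**The concern.** The same patient can fall under two rules that do not agree. Section 3.1.1.4 applies because the event is a Cycle 1 DLT; Table 3 or Section 5.1.2.2 applies because of the type and grade of the event. Section 4.3.2 sends sites to both: to Section 5.1.2 for dose modification, to Table 3 for infusion reactions, and to Section 3.1.1.4 for continued treatment.

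The patients concerned have just had a dose-limiting event in a first-in-human study. If sites resolve the conflict differently, similar patients may be re-dosed at different levels or after different degrees of recovery. Cycles received and dose intensity are listed in Table 1 of the protocol under the primary safety objective, and both would then depend partly on which section was followed. Section 6 summarizes by assigned dose level, so patients re-dosed under different rules would sit in the same column.

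**Working it through.** No figure in the plan needs reproducing. The check is to take each type of Cycle 1 DLT through both sets of rules.

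**1. Grade 3 infusion reaction without anaphylactic signs.** It is non-hematologic, Grade 3 and not among the exceptions in Section 3.1.1.1, so it is a DLT unless clearly attributed to another cause.
- Section 3.1.1.4: restart at a level tolerated by the prior cohort, after discussion with the Medical Monitor.
- Table 3: subsequent cycles at the same level, at the investigator's discretion.
- Result: explicit conflict on dose, and on who is involved in the decision.

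**2. Other drug-related Grade 3 or higher non-hematologic DLT, baseline Grade 0, recovered to Grade 1.**
- Section 3.1.1.4: baseline grade has not been reached, so the restart condition is not met. The Medical Monitor may lengthen the delay, but nothing there lowers the recovery requirement.
- Section 5.1.2.2: Grade 1 is sufficient and treatment may restart.
- Result: conflict on recovery. There is none on dose in escalation, since both call for a lower level.

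**3. Hematologic DLT, for example Grade 4 thrombocytopenia.**
- Section 3.1.1.4: return to baseline grade, then a level tolerated by the prior cohort.
- Table 3: resume at fixed counts. The reduced dose is tied to recurrence in consecutive cycles, which implies an unchanged dose at the first resumption.
- Result: conflict on the recovery test, and on dose by implication only. The ANC and platelet thresholds equal the entry minimums in Section 4.1.1 (1500 and 100,000/µL). The hemoglobin threshold of 8 g/dL is below the entry minimum of 9.0 g/dL. None refers to the patient's own baseline.

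**Precedence.** Section 5.1.2.2 states its relation to Table 3 by covering only toxicities not listed there. No comparable statement separates Cycle 1 DLTs from either. Section 5.1.2.1, to which Section 3.1.1.4 points, gives reduction and delay limits but no order of precedence.

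**Size of the dose difference.** Inputs are the Section 3.1 levels for Cohorts 1–5: 0.6, 1.2, 2.4, 4.0 and 6.0 mg/kg, with no patient in these cohorts to receive more than 2.4 mg/kg. The ratio is the same level divided by the adjacent lower level, after the cap:
- Cohort 2: 1.2 / 0.6 = 2.0
- Cohort 3: 2.4 / 1.2 = 2.0
- Cohort 4: same level 4.0 capped to 2.4, prior level 2.4; 2.4 / 2.4 = 1.0
- Cohort 5: same level 6.0 and prior level 4.0, both capped to 2.4; 2.4 / 2.4 = 1.0

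Cohort 1 has no prior cohort, so no ratio exists.

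**The case against.** The strongest reply is that Section 3.1.1.4 is the specific rule for Cycle 1 DLTs, while Section 5.1.2 offers guidelines for any cycle. The infusion-reaction and Section 5.1.2.2 wordings are permissive, so a site following the stricter section breaches neither. DLTs must be reported to the sponsor within 24 hours, which gives it a chance to intervene.

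Much of this is fair, but it does not settle the matter. Section 3.1.1.4 is specific by timing and Table 3 is specific by event, so neither is plainly the general rule. A site using the Table 3 permission in good faith departs from Section 3.1.1.4. The hematologic row is worded as an instruction to resume, not as an option. Reporting a DLT does not tell the site which rule applies.

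Some stronger readings are tempting and should not be taken:

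- **That Section 5.1.2.2 allows the same dose after a Grade 3 DLT.** Its current-dose restart is for Grade 2 events only.
- **That a patient still at Grade 1 on Day 14 must be discontinued under Section 3.1.1.4.** The Medical Monitor may extend the delay.
- **That the same-cycle wording in Table 3 is itself a conflict.** It can be read as finishing an interrupted infusion, which Section 3.1.1.4, on Cycles 2 and later, does not address. The conflict lies in the subsequent cycles.
- **That Table 3 states a same-dose restart for hematologic events.** This is inferred from where the reduction first appears.

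**Conclusion.** The inconsistency is real and more than a missing detail, because two written rules give different re-dosing for the same event. It is explicit on dose for Grade 3 infusion reactions, explicit on recovery for other related Grade 3 or higher toxicity, and partly implied for hematologic DLTs.

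Among the stated levels the dose difference is at most a factor of 2.0. A reader might compute 4.0/2.4 = 1.67 and 6.0/4.0 = 1.5 for the upper cohorts, but the 2.4 mg/kg cap rules those doses out. This takes the prior cohort's level to be the adjacent lower one. The visible text gives no levels beyond Cohort 5.

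A reader might also infer that the MTD determination is compromised. The documents do not support that: the DLT is counted before any restart, so DLT counts, 3+3 decisions and Tables 6–8 stand. The consequences are for patient safety at re-dosing and for cycles received and dose intensity. These are descriptive endpoints, and Section 6.4 flags dose modifications. The problem mainly concerns escalation patients, because Section 3.1.2 carries only the acceptable-toxicity and clinical-benefit criteria into expansion. Left ventricular DLTs could not be checked, as the content of Figure 2 is not shown in the text available.

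**What to change.** Reconcile Section 3.1.1.4, Section 5.1.2.2 and the two Table 3 entries (Grade 3 infusion-related reaction or hypersensitivity, and hematologic toxicity). In one place, state which rule governs an event that is a DLT in the Cycle 1 window, covering both the recovery threshold and the restart dose, and whether the Medical Monitor must be consulted. Cross-refer to that statement from the other sections. The sponsor's clinical team must choose the rule; no view is offered here on which is right. The cost is a few sentences and cross-references in an amendment, with no added patients or procedures and no change to the statistical design.
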